9.1 Institutional Review Board

The Study Protocol, Investigator Brochure, consent form, Investigational New Drug application (IND) and other relevant documents will be submitted to the UMass IRB for approval prior to commencement of the trial. Any amendment other than minor administrative changes, must be reviewed and approved by the IRB before implementation.

9.2 Food and Drug Administration

Use of ifetroban in this clinical trial is covered under an approved IND application to the US Food and Drug Administration (FDA).

9.3 Independent Clinical Event Adjudicator

An independent Clinical Event Adjudicator, with expertise in the field of cardiology will be identified and trained on the study protocol and Investigator Brochure prior to the first subject enrollment in this study. The role of this CEA is to provide an independent, expert review of data on clinical events based on protocol specific definitions outlined below.

9.4 Adverse Events

9.4.1 Definitions

9.4.1.1 Adverse Event

An adverse event (AE) is any untoward medical occurrence associated with the use of a drug in a participant, whether or not considered drug or biologic related. An AE can therefore be any undesirable sign, symptom or medical condition occurring after starting study drug, even if the event is not considered to be related to the pharmaceutical product. Study drug includes the drug under evaluation, and any reference or placebo drug given during any phase of the trial.

9.4.1.2 Suspected Adverse Reaction

A suspected adverse reaction (SAR) is any adverse event for which there is a reasonable possibility that the drug caused the event. “Reasonable possibility” suggests there is a causal relationship between the drug and the adverse event. “Suspected adverse reaction” implies a lesser degree of certainty about causality than adverse reaction, which means any adverse event caused by a drug.

9.4.1.3 Serious Adverse Events (SAE)

An adverse event or suspected adverse reaction is considered serious if the investigator or sponsor believes any of the following outcomes occurred:

- Death
- Life-threatening AE: Places the participant at immediate risk of death at the time of the event as it occurred. It does not include an AE that, had it occurred in a more severe form, might have caused death.
- Persistent or significant incapacity or substantial disruption of the ability to conduct normal life functions.
- Inpatient hospitalization or prolongation of hospitalization.
- Results in congenital anomaly or birth defect.
- Important medical events that may not result in death, be life threatening, or require hospitalization may be considered a serious adverse event when, based upon appropriate medical judgment, they may jeopardize the participant and may require medical or surgical intervention to prevent one of the outcomes listed in this definition above. This determination is based on the opinion of either the investigator or sponsor (e.g., if either believes it is serious, it must be considered serious).

9.4.1.4 Laboratory Test Abnormalities

For laboratory test abnormalities that meet the definition of an SAE, that required the participant to have the investigational product discontinued or interrupted or required the participant to receive specific corrective therapy, the clinical diagnosis rather than the laboratory term will be used by the reporting investigator (e.g., anemia versus low hemoglobin value).

9.4.1.5 Assessment of Causal Relationship

A medically-qualified investigator must assess the relationship of any AE to the use of study drug, based on available information, using the following guidelines:

- **Not related:** There is not a reasonable causal relationship to the investigational product and the adverse event.
- **Unlikely related:** No temporal association or the cause of the event has been identified, or the drug or biologic cannot be implicated.
- **Possibly related:** There is reasonable evidence to suggest a causal relationship between the drug and adverse event.
- **Related:** There is evidence to suggest a causal relationship, and the influence of other factors is unlikely.

9.4.1.6 Assessment of Adverse Event Severity

The determination of adverse event severity rests on medical judgment of a medically-qualified Investigator. The severity of AEs will be graded using the following definitions:

- **Mild:** Awareness of sign, symptom, or event, but easily tolerated.
- **Moderate:** Discomfort enough to cause interference with usual activity and may warrant intervention.
- **Severe:** Incapacitating with inability to do usual activities or significantly affects clinical status and warrants intervention.

9.4.1.7 Expectedness

The expectedness of an AE or SAR shall be determined according to the most current Investigator's Brochure. Any AE that is not identified in nature, severity, or specificity in the current investigator's brochure is considered unexpected. Events that are mentioned in the Investigator's Brochure as occurring with a class of drugs or as anticipated from the pharmacological properties of the drug, but not specifically mentioned as occurring with the particular drug under investigation are considered unexpected.

9.4.2 Recording and Reporting of Adverse Events

The principal investigator, CEA and study team are responsible for monitoring the safety of participants enrolled into the trial. Events significant enough to necessitate discontinuation of study drug dosing will be captured on the AE electronic case report forms (eCRF).

All AEs/SAEs, except for those anticipated AEs, occurring from signed informed consent to 14 (+/- 3 days) after visit 3 will be captured on the AE/SAE eCRF. Unless exempted, all SAEs, whether or not deemed drug-related or expected, must be reported by the investigator or qualified designee within 24 hours of first becoming aware of the event. For this study, all deaths will be reported on the SAE eCRF, as well as the Death eCRF page. The investigator or qualified designee will enter the required information regarding the AE/SAE into the appropriate module of the eCRF, which will be shared with the CEA.

When additional relevant information becomes available, the Investigator will record follow-up information according to the same process used for reporting the initial event as described above. The Investigator will follow all reportable events until resolution, stabilization or the event is otherwise explained. The investigators are also responsible for promptly reporting SAEs to the IRB per our institutional policy..

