9.4.3 Suspected Unexpected Serious Adverse Reaction

AEs that meet the criteria of serious, related to study drug, and unexpected per the Investigator's Brochure, qualify for expedited reporting to the regulatory authorities. The PI will notify the FDA and all participating investigators in a written IND safety report of an SAR that is serious and is unexpected, based on the opinion of the Adjudicator as soon as possible, but not later than 15 calendar days after the event is confirmed to be a serious, unexpected SAR and qualifies for expedited reporting.

10 Statistical Considerations

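### Section 9.4.2 keeps an unbounded class of 'anticipated' adverse events off the AE/SAE form, so non-serious events, possibly including known drug effects, can be missing from the safety record

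*Combined protocol and SAP*

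**What the plan says.** The rule in 9.4.2 for the AE/SAE form reads "All AEs/SAEs, except for those anticipated AEs, occurring from signed informed consent to 14 (+/- 3 days) after visit 3 will be captured". The same section has a separate rule for events that end treatment: "Events significant enough to necessitate discontinuation of study drug dosing will be captured on the AE electronic case report forms". It requires all deaths to be entered on both the SAE and the Death pages.

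For serious events 9.4.2 says: "Unless exempted, all SAEs, whether or not deemed drug-related or expected, must be reported by the investigator or qualified designee within 24 hours", counted from awareness. It adds: "The investigators are also responsible for promptly reporting SAEs to the IRB per our institutional policy". AE and SAE information is entered "into the appropriate module of the eCRF, which will be shared with the CEA", the Clinical Event Adjudicator.

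Section 9.4.1.1 defines an AE broadly, whether or not it is related to the drug, and describes it as arising after study drug has been started. Section 9.4.1.7 defines expectedness by the Investigator's Brochure and says that events described there "as anticipated from the pharmacological properties of the drug, but not specifically mentioned as occurring with the particular drug under investigation are considered unexpected". Section 9.4.3 reserves expedited reporting for "AEs that meet the criteria of serious, related to study drug, and unexpected" per the Brochure.

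**The concern.** Section 9.4.2 does more than leave a term undefined. It states a rule that removes a class of events from the form, and it does not say which events belong to the class. The wording points to a list, but no list is given. Whoever completes the form must decide what counts as anticipated, and an event so judged may be omitted.

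At stake is the completeness of the non-serious safety data in a placebo-controlled trial. Under some readings the omitted events would include known effects of ifetroban. Scheduled safety assessment is otherwise mainly physical examination and vital signs (Protocol Summary), so the AE form carries much of what the trial will learn about tolerability over the four weeks of treatment.

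**Working it through.** No arithmetic applies. The check sets the relevant sections side by side.

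1. **Is the category defined?** Sections 9.4.1.1 to 9.4.1.7 cover the AE, the suspected adverse reaction, the SAE, laboratory abnormalities, causality, severity and expectedness. None defines an anticipated AE or an exempted SAE. Appendix A schedules AE assessment but lists no excluded events.

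2. **Does the AE definition imply the exception?** No. Section 9.4.1.1 takes in any untoward occurrence and carves nothing out, so the exception arises only in 9.4.2.

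3. **Can 'anticipated' be read as 'expected'?** Section 9.4.1.7 treats certain events "as anticipated from the pharmacological properties of the drug, but not specifically mentioned as occurring with the particular drug under investigation are considered unexpected". An event can therefore be anticipated and unexpected at once. Section 9.4.2 also uses the word expected in its next sentence, on SAEs, which suggests that a different word was meant. Sections 9.4.1.7 and 9.4.3 cite the Brochure where they rely on it; 9.4.2 does not cite it for this exception.

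4. **Which readings remain?**
   - *Procedural effects only.* Sections 6.6.1.2 and 6.6.1.3 name puncture-site bleeding, bruising, pain and cuff discomfort as risks, but do not call them anticipated AEs or exempt them from recording. Both arms have the same procedures, so little would be lost.
   - *Events listed in the Brochure.* Known drug effects would then be left off the form.
   - *Events foreseeable from pharmacology.* Possible drug effects would then be left off, including some that 9.4.1.7 classes as unexpected.

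5. **What is captured under every reading?** Deaths, events that stop study drug and SAEs not exempted. The events exposed to the rule are therefore non-serious ones that do not stop study drug.

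6. **The SAE qualifier, taken separately.** The opening words of "Unless exempted, all SAEs, whether or not deemed drug-related or expected, must be reported by the investigator or qualified designee within 24 hours" presuppose exemptions, and none is stated. They concern 24-hour reporting of serious events and lend no support to the point about non-serious ones. Section 9.4.2 cites institutional policy only for reporting SAEs to the IRB.

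7. **Start of the window.** Section 9.4.1.1 places an AE after study drug is started; 9.4.2 records from signed consent. In 4.3.1 the baseline blood samples and vascular tests are listed before randomization and dispensing. An effect of those procedures falls inside the 9.4.2 window but outside the wording of 9.4.1.1.

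**The case against.** The strongest reply is that this is a wording gap with little consequence. Leaving foreseeable procedural effects off an AE form is a legitimate choice, and a short list would make it clear. AEs are not an endpoint, and neither the Protocol Summary nor 10.2 plans an AE comparison by arm. The trial is single-centre and double-blind, so recording practice should vary less and knowledge of allocation should not drive it. Appendix A has AEs assessed at Visits 1 to 4, so events are still asked about. Most of this stands, and it limits the consequence. It does not answer the main point: blinding does not restore an event that was never entered, and the text does not confine the exception to procedural effects.

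A reader might infer more than the documents support:

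- *That serious events will be lost.* SAEs are reportable regardless of relatedness or expectedness apart from the unstated exemption, all deaths are entered, and SAEs also go to the IRB.
- *That the arms will be recorded differently.* Nothing in a blinded, single-centre process points to a difference by allocation, although omitted drug effects would not be recovered.
- *That bleeding on ifetroban is exempt.* No section calls drug-related bleeding anticipated; 6.6.1.2 mentions bleeding and bruising only as blood-draw risks.
- *That oversight is defeated.* The audit in 12.4 covers FDA regulations and investigator obligations as well as the protocol. On the Adjudicator, 9.3 says "The role of this CEA is to provide an independent, expert review of data on clinical events" using protocol definitions, and the one decision assigned in 9.4.3 concerns serious unexpected reactions. Omitted non-serious events would not reach the Adjudicator through the eCRF, but they are not shown to matter to that decision.

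**Conclusion.** The concern holds in a limited form. The exception in 9.4.2 has no stated bounds, conflicts with the breadth of 9.4.1.1, and cannot be filled in from 9.4.1.7. Applied as written, it allows non-serious events that do not stop study drug to be left off the form in both arms, possibly including known drug effects.

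The size cannot be estimated. The documents give no rates for minor events, and the Investigator's Brochure is not available here. The loss is small if only procedural effects are meant and larger under the other two readings. The primary RHI analysis is untouched. The conclusion assumes that no definition outside the protocol governs the exception; 9.4.2 points to none.

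The change should be made because it is cheap and improves the safety record, not because harm has been shown. The SAE exemption and the start of the window are separate, smaller drafting points.

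**What to change.** - **Main change.** In 9.4.2, delete the clause excepting anticipated AEs, so that every AE in the stated window goes on the AE/SAE eCRF. Use expectedness only to decide expedited reporting under 9.4.3.
- **Fallback.** If an exception is kept, write a closed list of the excluded events into 9.4.2. This removes the ambiguity, but the listed events still go unrecorded.
- **SAE exemption.** Remove the qualifier on 24-hour SAE reporting, or cite the policy that defines the exemption.
- **Start of recording.** Reconcile 9.4.1.1 with 9.4.2, so that it is clear whether events between consent and the start of study drug are AEs to be entered.

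The cost is some additional eCRF entries, partly trivial, for at most 57 subjects, with no added visit or procedure. Section 6.6.1.2 expects blood-draw effects in only a very small share of subjects; no frequency is given for cuff discomfort, so that part of the burden cannot be stated exactly.

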9.4.3 Suspected Unexpected Serious Adverse Reaction

AEs that meet the criteria of serious, related to study drug, and unexpected per the Investigator's Brochure, qualify for expedited reporting to the regulatory authorities. The PI will notify the FDA and all participating investigators in a written IND safety report of an SAR that is serious and is unexpected, based on the opinion of the Adjudicator as soon as possible, but not later than 15 calendar days after the event is confirmed to be a serious, unexpected SAR and qualifies for expedited reporting.

10 Statistical Considerations

10.1 Sample Size Calculations

10.1.1 Primary Endpoint

Data from several studies was used to determine the power to detect a difference in RHI with drug treatment. In one study of PAT reproducibility in cardiovascular patients, the intra-patient standard deviation was 0.31.⁵⁵ In a meta-analysis of >1500 subjects with cardiovascular disease the mean RHI was 1.52.⁵⁶ Based on these data, a sample size of 48 total subjects (24 randomized each to ifetroban or placebo) is required to detect a 20% increase in RHI with over 85% power with a two-sided alpha of =0.05. Adjusting for 10% loss to follow up, we will need 52 randomized subjects.

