Study Design	
This is a phase 2b, single center, prospectively randomized, double-blinded, placebo-controlled clinical trial conducted at the UMass Medical School/UMass Memorial Medical Center.
 
Subjects with cardiovascular disease on standard aspirin therapy with elevated non-platelet thromboxane generation defined by urine thromboxane B₂ metabolites >1145 pg/mg creatinine will be randomized to receive either ifetroban 250 mg capsules once daily or matching placebo.

Number of Subjects	57 subjects randomized 1:1 to ifetroban or placebo.
Treatment Duration	4 weeks
Study Endpoints	The primary trial endpoint will be the change from baseline in Reactive Hyperemia Index (RHI) measured by peripheral arterial tonometry (PAT).

	
Secondary trial endpoints will be the change from baseline in on-treatment: 1) % flow-mediated vasodilation (FMD),and; 2) urine 11-dhTXB₂.
 
Exploratory trial endpoints will be the change from baseline in on-treatment: 1) urine 8-iso-PFG_{2α}; 2) plasma tissue factor; 3) plasma ICAM-1; 4) plasma activated protein C; 5) hs-CRP; 6) NT pro-BNP; 7) urine 2,3-dinor-6-ketoPGF_{1α} and ratio of 11-dhTXB₂ to 2,3-dinor-6-ketoPGF_{1α}; 8) urine TXB₂, 6-ketoPGF_{1α} and the ratio of TXB₂ to 6-ketoPGF_{1α}, and; 9) glomerular filtration rate.

Inclusion Criteria	
Males and females 18-80 years of age with established cardiovascular disease who take ≥81 mg daily of aspirin and have thromboxane B₂ metabolites >1145 pg/mg creatinine on screening.
 
Able to provide written consent and comply with protocol-specific procedures.

Exclusion Criteria	
Chronic oral anticoagulation with non-vitamin K antagonist.
 
Anticipated change or interruption in aspirin therapy during the study period.
 
ST segment myocardial infarction within the past 30 days.
 
Cardiac surgery within the past 30 days.
 
Stage 4-5 renal failure or on renal replacement therapy.
 
An ongoing uncontrolled severe inflammatory condition.
 
Pregnant, intending to become pregnant or breast feeding.
 
Known ifetroban or aspirin sensitivity
 
Inability to perform vascular testing.
 
Participation in another investigational drug trial within 30 days of randomization.

Safety Evaluation	
Safety assessments will be performed at all study visits and will include physical examination and vital signs (blood pressure, pulse rate, respiration rate).

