6.2 Estimated Enrollment Period

This study will enroll a maximum of 57 subjects over a period of 30 months.

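### Section 10.1.1 requires 52 randomised subjects, the Protocol Summary says 57 are randomised, and 57 is not derived anywhere

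*Combined protocol and SAP*

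**What the plan says.** The sample-size argument for the primary endpoint is in section 10.1.1. It concludes that "a sample size of 48 total subjects (24 randomized each to ifetroban or placebo) is required to detect a 20% increase in RHI", and then moves from evaluable to randomised subjects in one sentence: "Adjusting for 10% loss to follow up, we will need 52 randomized subjects".

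The total appears in two other places. The Protocol Summary, under Number of Subjects, reads "57 subjects randomized 1:1 to ifetroban or placebo". Section 6.2 reads "This study will enroll a maximum of 57 subjects over a period of 30 months".

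Section 10.1.2, on the secondary endpoints, also works with 48 subjects. It makes no allowance for loss and gives no other total.

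**The concern.** Section 10.1.1 and the Summary count the same thing, subjects randomised, and give different numbers. Section 6.2 alone would not conflict with 52, because a ceiling can sit above a requirement. The Summary line carries no such qualifier: it gives 57 as the number randomised.

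The number to randomise is a basic design figure. As the text stands, a reader cannot say whether recruitment is complete at 52 or at 57, or what loss rate 57 is meant to absorb. The protocol gives no other rule for ending enrolment, so stopping anywhere from 52 to 57 could be described as following the plan.

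There is also a smaller arithmetic point. The figure of 52 does not deliver the 48 completers it is meant to secure at the stated loss rate.

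**Working it through.** **Inputs.** Evaluable subjects: 48, or 24 per arm (section 10.1.1). Loss to follow-up: 10% (section 10.1.1). Allocation: 1:1 (Protocol Summary, section 4.2). Stated randomised totals: 52 (section 10.1.1) and 57 (Protocol Summary).

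**Step 1: reproduce 52.** Multiplying up gives N × (1 + d) = 48 × 1.10 = 52.8. Truncating gives 52, and rounding up gives 53. The plan's figure is therefore probably 48 × 1.10 with the fraction dropped.

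**Step 2: the usual inflation.** To have N left after a loss d, randomise N/(1 − d) = 48/0.90 = 53.3, so 54. Per arm, 24/0.90 = 26.7, so 27, and 2 × 27 = 54.

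**Step 3: what each total leaves.** Completers at 10% loss are total × 0.90. The largest loss that still leaves 48 is 1 − 48/total.

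| Randomised | Completers at 10% loss | Losses that still leave 48 |
|---|---|---|
| 52 | 46.8 | 4 (7.7%) |
| 54 | 48.6 | 6 (11.1%) |
| 57 | 51.3 | 9 (15.8%) |

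So 52 falls 48 − 46.8 = 1.2 subjects short and tolerates only 7.7% loss, not the 10% it is said to cover.

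**Step 4: can 57 be reached?** Not from 48 and 10%, which give 52.8 or 53.3 before rounding. Two undocumented routes come close: 48/0.85 = 56.5, which rounds up to 57 and would mean a 15% loss, and 52 × 1.10 = 57.2, which would apply the 10% twice. The document states neither, so the origin of 57 is unknown.

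**Step 5: the split of 57.** An odd total cannot divide equally. The nearest split is 28 and 29, and the smaller arm keeps 24 after 4 losses (1 − 24/28 = 14.3%).

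**The case against.** The best defence is that the numbers answer different questions: 52 is what the statistics need, 57 is the most that will be enrolled, and the Summary line is a loose restatement of the section 6.2 ceiling. On that reading, randomising up to 57 satisfies the need for 52. This is a plausible account of what was intended, but the Summary line does not say it, and nothing explains why the ceiling is 57. The inconsistency in the text stands.

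A second point is that moving from 52 to 54 is partly a matter of convention, since 48 × 1.10 is a common shortcut. The shortcut does explain the figure, but it gives 52.8, and a required sample is rounded up. Under either convention 52 is too low, by one subject or by two.

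Third, the shortfall hardly matters for power on the plan's own inputs. Take the difference as 20% of 1.52 = 0.304 and the SD of 0.31 at face value. A two-sided t-test then has 91.4% power with 24 per arm, 90.2% with 23 and 85.6% with 20, so 46.8 completers still meets the stated goal of over 85%. This is accepted, and it is one reason the point is minor.

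Finally, 1:1 is an allocation ratio and does not promise equal arms. The odd total is therefore a side remark and not a fault in its own right.

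**Conclusion.** The point holds and is minor. The plan gives two randomisation totals that differ by 5 (52 and 57), and 57 has no derivation in the document as supplied. Separately, 52 is 1.2 completers short of the required 48 at the stated 10% loss.

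The consequence is limited because the larger number errs on the safe side: 57 leaves about 51 completers at 10% loss and keeps 48 at up to 15.8%. The conclusion rests only on the plan's figures of 48 evaluable subjects and 10% loss. It makes no claim about whether 48 is adequate for the primary endpoint or for flow-mediated dilation.

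**What to change.** Give one randomisation target, with its derivation, consistently in the Protocol Summary, section 6.2 and section 10.1.1. Either of two edits would do:

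- **(a)** In section 10.1.1, replace 52 with 54 (48/0.90 = 53.3, rounded up; 27 per arm). In the Summary and section 6.2, describe 57 as an enrolment ceiling.
- **(b)** In section 10.1.1, replace 52 with 57 and state the loss it allows for: about 51 completers at 10% loss, and 48 retained at up to 15.8%. Give the intended arm sizes as 28 and 29, noting that the split achieved depends on how the randomisation is balanced.

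The cost is a text correction in up to three places. Neither option needs subjects beyond the 57 already stated.
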